## Population description and sample selection

### **Study location:**

Acatlán de Juárez is a small town and municipality in the central region of the state of Jalisco state, Mexico. It is located approximately 45.7 km south of Guadalajara, in the Lagunas region. It has an area of 176.85 km^2. According to the 2010 census, it has a population of 23,241 inhabitants, of which 9.88% are children between 6 and 10 years old. The main economic activities are agriculture of cane, corn, beans, peanuts, sunflower, and tomatoes. Within the cattle raising, the main breeding is from dairy and beef cattle, pigs, sheep, goats, horses, and various birds, beehives, and rabbits; the main branches of the Acatlán de Juárez industry are sugar and alcohol. For commerce, the municipality counts with various commercial establishments, where one can find basic necessities. There are five medical units and 11 elementary schools (Gobierno del Estado de Jalisco, 2015; Instituto Nacional de Estadística y Geografía, 2010).

### **Selection of study schools:**

The strategies will be implemented in all three intervention schools. A nutrition diagnosis will be offered as a community service to the rest of the schools in Acatlán de Juárez in a previous stage of the study; none of the described strategies will be implemented. The schools were chosen at the convenience of the size of the student body. In addition to having a sufficient population, each school's authorities needed to be willing to participate.

### **Selection of control schools:**

There were three elementary schools selected from the municipality of comparison (Villa Corona, Jalisco). The schools were chosen for their similarities in social, economic, and geographic contexts to the intervention municipality. These schools were selected for the similarity in the student body size for the intervention schools.

### **Subjects of study:**

Depending on the different strategies, it is pretended to incorporate:

- Children from six to ten years of age (completed at the beginning of the study) who attend public schools from the intervention community

- Mothers and fathers from families with kids of school-age
- Personnel in charge of school cooperatives
- Key actors and members of different groups involved in the implementation of the strategies.

**Sample size:**

All schools and retail outlets of food in and around the schools will be evaluated. The anthropometric measures (height, weight, waist, and three basic folds) will be taken from students from 1st to 4th year of elementary schools.

For the calculation of the sample size, data of a similar study realized by Li and Col. were used. In 2014 (Li et al., 2014), a total sample size of 288 children among the six schools (three control and three intervention) took into account a loss in the follow-up of 30%. It was considered a type I error of .05, power of 80%, and six clusters.

## Selection of the sub-sample

One cluster will be randomly selected from each grade level of the schools chosen, listed in Table 1, and within each cluster chosen, 12 children will be randomly selected per cluster (48 children total per school)

**The exclusion criteria are:**

- Chronic disease with confirmed diagnosis (Cancer, diabetes type 1 or type 2)
- Physical limitations that could affect the development and standard nutritional patterns.
- Use of medications that may influence energy consumption and expenditure (antidepressant drugs, antipsychotics, and steroids).
- Children who are or have been in a weight reduction program in the past year.
- Use of medications or confirmed diagnosis of illnesses that could alter laboratory values.

## Fieldwork logistics in evaluation periods

The field strategy for information gathering in the three evaluation periods will be organized with a single brigade of six people (during the evaluation periods, there will be two more people to complement the 6-member brigade and facilitate the collection of information; while four members will stay in the project during the implementation of strategies). In addition, some of the project's researchers and undergraduate nutritionists will participate as support in the measurement period. The brigade will work in each of the schools for approximately one week, starting with the intervention schools. It is expected that in 2 months, all the required information will be completed. The responsibilities will be distributed inside the brigade to optimize the time. The qualitative component will be implemented by different brigade personnel to ensure their specialization in qualitative methodologies. The project will count with one general field supervisor to ensure that the brigade personnel is advised and supported at all times.

Field staff will receive the appropriate training in interviewing techniques, ethical considerations, filling out specific questionnaires, training in the anthropometric measures, and blood pressure. One researcher will be trained in the SOFIT method. Only the standardized personnel with the specific techniques will be responsible for gathering the information.

### **Blood sampling**

Glucose and lipid determinations on blood will be made by the laboratory of clinical analysis of the University Center of Exact Sciences and Engineering (CUCEI; in Spanish Centro Universitario de Ciencias Exactas e Ingeniería) of the University of Guadalajara, who will be going to the schools, take the samples, analyze them and deliver the results. The determination of blood chemistry analytes is done by spectrophotometry in liquid chemistry. The hematic biometry is done with the SISMEX equipment by impedance. The laboratory is registered on the external quality control PACAL (Quality Assurance Program) company certified in ISO 9001:2008 and certified by System ISO 9001. In addition, it has Notice of Laboratory Operation at the Jalisco Ministry of Health and the University of Guadalajara. They are also registered with the Ministry of Environment and Natural Resources (SEMARNAT. In Spanish: Secretaría de Medio Ambiente y Recursos Naturales) and have transportation and reception of biologically hazardous waste with the company Corporate

Techno Ambienta. For the collection of blood samples, children and their parents will be asked to have fasting of food and caloric beverages for 12 hours before intake (usually the night before), which must be suspended as soon as the measurement is made. The blood samples collection will be conducted on school premises by qualified CUCEI staff (described at the beginning of this section) at the end of the baseline, intermediate, and final measurement period. It is estimated that the measurements are taken during the first hours of the school day (between 8:00 and 10:00 hours), and approximately 10 ml of blood will be taken per child.

## Action strategies

### Strategy implementation

The strategies of the project are aimed to improve nutrition and increase the physical activity of the children. They are mainly based on the implementation of the guidelines of the "National Strategy for the Prevention and Control of Overweight, Obesity, and Diabetes" in a guided and supervised way by the research team of this project; In addition, it is intended to incorporate strategies suggested by the own community of intervention. In the control community, as in the rest of the country, it is expected that the actions of the "National Strategy for the Prevention and Control of Overweight, Obesity, and Diabetes" are gradually implemented under the capacities of local authorities in education and health.

In both intervention and control communities, results will be presented by the school after each measurement period, and parents will be given the results of their child's nutritional status.

To achieve a better acceptance of the strategies by the population in the intervention locality, these will be implemented in collaboration with municipal authorities, schools, parents, and staff from ITESO, UdeG, and AJANUT. The aim is to involve the key actors of both the school environment and community, from early stages of the project, in order to adapt the strategies to be cultural and socially acceptable, generating strategies that could contribute to the achievement of the goals and promote the appropriation of the project from the community. Key actors include parents, school principals, teachers, food service concessionaires within the school grounds, and municipal authorities of Acatlán de Juárez in contact with the school-age children from six to ten years old.

Initially, the strategies to be implemented will include the following:

- Regulation of food sales within school grounds
- Awareness of children, parents, teachers, and staff in charge of the food supply to improve acceptance and commitment to food sales regulation.
- Training of staff in charge of food supply within the school, to help support the preparation of healthy foods.
- Promotion of the consumption of water.
- Organization of events and support in the coordination of groups that promote physical activity at the community level.
- Implementation of healthy spaces inside the school
- Improve the quality of the physical education classes within schools
- Physical activities outside school hours and during vacations to promote physical activity all year round.
- Offering different types of support for the implementation and promotion of health care actions within the school context.
- Development of skills in the educational community for health care and the generation of healthy school environments.
- Creation and/or strengthening of health and nutrition committees in schools, with school principals, teachers, and parents to generate primary conditions that favor healthy environments.

Table 5 lists possible intervention strategies taken from the study realized before in Tlaltizapan, Morelos; however, in the current project, some strategies may be modified once the result of the formative investigation and viability are known.

For the implementation of the strategies, the population will be actively involved; it will be established on a common agreement the times, responsibilities, and activities for the organization and convening of courses and events. The research team will design the contents and didactic materials for the courses and workshops, considering the community's opinions and suggestions.

Table 5 Description of strategies proposed in the previous project carried out in Tlaltizapan, Morelos

Strategy	Implementation
Regulation of food sales on school grounds	Compliance with food sales guidelines in schools will be monitored. Non-compliance will be reported to school principals and they will be encouraged to limit sales to permitted products, advising those in charge to do so.
Awareness of children, parents, teachers and staff in charge of food offering to improve the acceptance and commitment to the regulations	
There will be an opening event at the beginning of the project activities, which will include the community and various recreational activities that promote healthy food and physical activity.
 
Meetings will be held with parents and teachers to explain in detail the purpose of the regulation, the process of elaboration of the guidelines, to make known the benefits of good nutrition, the risks of consuming food that is dense in calories and high fat content, and answer questions about it.
 
Similar guidance will be provided to food sales staff but during the time of the school day, with the help of the teachers. They will be informed that they will be able to access workshops and training to adapt their food supply to the guidelines.
 
Children will have an explanation during classes, complementing the nutrition content marked by SEP. Each group will be asked for a space to explain the new regulations and to answer their questions about them.

Training of the staff in charge of the food offer in the schools, to support the preparation of healthy food	Free workshops will be provided to adapt the food supply to the guidelines. The main topics to be discussed will be portion sizes, healthy cooking methods, hygiene in the preparation and healthy ingredients. It is aimed to offer the workshops for each school, on campus, and at times that result convenient to vendors. To integrate food vendors from around the schools, the support of the Municipal President will be sought.
Organization of events and support in the coordination of groups that promote the physical activity at the community level.	In coordination with the key actors, support will be given to the organization of sports tournaments, walks, dance competitions, etc. (depending on children's preferences). Schools will be

	
supported in the purchase of some games that encourage physical activity that can be used by all children during recess.

Improve the quality of physical education classes on school campuses	
Physical education teachers will be provided with manuals for class development of physical education adapted to the Mexican context. As an additional tool to existing classroom programs.
 
Each group will be monitored to take at least 2 physical education classes per week and the effective time of each class. Principals will be encouraged to comply with the regarding physical education classes.

Implementation of healthy spaces on school campuses	
In coordination with local key actors, actions such as food fairs, healthy lunch contests, gastronomic exhibitions or conferences, nutrition week, etc. will be organized.

Physical activation outside of class and outside of the school calendar (Not applicable in Tlaltizapan)	
Activities will be planned so that children can go to their schools (or community centers) outside of their school hours and during vacations to stay active even at times outside of their school hours. For the above, the support of social service providers of the Bachelor of Physical Culture and Sport (or similar) will be sought.

To offer diverse support for the implementation of health promotion and care actions in the school context	
Courses will be developed for teachers to give them useful tools in the health and nutrition sessions that they must give to their students as part of the modifications to the school curriculum that SEP has made. These courses will be based on the contents of the official textbooks. It will be coordinated with the school zone supervisor and with the principals of each school on the schedules and duration of the courses; and if possible, incentives or recognition to the teachers.

Creation and/or strengthening of health and nutrition committees in schools, with the participation of principals, teachers and parents to generate basic conditions that favor healthy environments.	
The formation of committees will be encouraged in schools where they have not been previously integrated. The support of the principals of each school will be requested for the invitations. A member of the project team will join each school's committee and participate in the meetings.

During the periods of strategy implementation, the project will have four people who will stay permanently in the locality for the duration of the intervention. A member of the project will be permanently in charge of implementing and monitoring the strategies at one of the community interventions schools, keeping direct contact with key actors. The same person will be a member of the health and nutrition committee of the school. In addition, monitoring activities will be carried out in the comparison schools, which will be systemized into indicators for the evaluation process. On the other hand, it is contemplated the support of nutritionists and other undergraduate professionals to support the elaboration of material, application of interventions, events, workshops, and measurements, with previous training and standardization.

Additionally, formative research will enrich the proposed strategies. This will be carried out with the support of personnel specialized in qualitative methodologies. Two people will be in charge of implementing the qualitative component, which will consist of non-participating observation, focus groups, and semi-structured interviews with children and key actors (parents, teachers, school principals, municipal authorities, and community leaders); to inquire about opinions, prejudices, and beliefs regarding the implementation of the guidelines that regulate food sales within school grounds. The same staff will be responsible for analyzing the information and determining the barriers and possible solutions to improve eating habits and encourage physical activity in the population (during the qualitative instruments' application, one more person will be supporting the research team). The focus group among children will be held inside the schools, working mainly with fifth and sixth-grade students. In addition, all teachers at each school will be invited to participate in a focus group that will be held at the school campus with the support of the principals. Semi-structured interviews will be conducted with children, parents, and teachers. The specialized staff in qualitative methodologies will personally arrange with each of the interviewees the day, time, and place where interviews will be held, supporting the interviewees' convenience.

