## Monitoring and evaluation

Table 6 describes the outcome variables. The conceptual framework of obesity causes (Figure 1) specifies a wide variety of factors that influence this pathology's immediate causes. To modify these factors, it is necessary to implement strategies that will impact the outcome variables, but whose impact is not direct. These strategies are mainly oriented towards modifying the food supply, increasing opportunities to make physical activity,

creating healthy environments, and community participation, among others; not precisely modifying the body composition. Many of the strategies proposed for the project will reflect on the outcome variables; however, their monitoring during the intervention will be given through process indicators, among which stand out:

- Number of parent's reunions, for each topic of health and nutrition
- Number and percentage of parents that assist the reunions about topics of health and nutrition (total of parents per group/number of parents that assist per group)
- Number of events outside school hours realized with health and nutrition topics
- Number of sports events realized
- Number of assistants and participants on sports events and health and nutrition topics
- Effective classes of physical education per group (physical education classes programmed per group / physical education classes realized per group)
- Duration pf physical education classes (minutes)
- Application grade of the guidelines
- Number of non-recommended foods present at the school campus

These are some of the indicators proposed; however, with the formative and viability investigation results, it will be possible to propose various actions for which indicators of the specific process will be designed.

During the implementation of the strategies, detailed records will be kept of relevant related events that may affect food and physical education dynamics in the schools and the locality (Table 4), both in the intervention and control localities. Similarly, a detailed registry will be kept of the agreements reached in meetings with key actors and the support given by the municipality and school authorities.

*Table 6 Outcome variables*

Category			
Basic causes			Underlying causes
Diet	Physical activity	Interpersonal factors	Environment
Energy consumption	Number of steps	Beliefs	Availability and accessibility of food and beverages
Fat consumption	Speed	Knowledge	Quality of infrastructure for physical activity and meals

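### The physical-education class indicator is written upside down and scaled to each group's own timetable, so it cannot show whether the stated standard of 2 classes per week is met

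*Protocol*

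**What the plan says.** The standard is in Table 5 (Action strategies, Strategy implementation), in the row on improving physical education: "Each group will be monitored to take at least 2 physical education classes per week and the effective time of each class". The same row adds "Principals will be encouraged to comply with the regarding physical education classes"; a noun is missing from that sentence, so what principals are to comply with is not stated.

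The indicator is in Monitoring and evaluation. That section says of the strategies that "their monitoring during the intervention will be given through process indicators, among which stand out", and the list includes "Effective classes of physical education per group (physical education classes programmed per group / physical education classes realized per group". The other physical-education entry is "Duration pf physical education classes (minutes". The list ends with "These are some of the indicators proposed; however, with the formative and viability investigation results, it will be possible to propose various actions".

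For the control arm, Strategy implementation says that "monitoring activities will be carried out in the comparison schools, which will be systemized into indicators for the evaluation process". The Information analysis plan places process indicators in their own results section and in six-month reports to the funder, apart from the impact results.

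**The concern.** Table 5 states delivery as a count per week. The indicator states it as a ratio of two counts, neither of which is fixed at 2. A reader of the process results who sees a value of 1 would take it as full delivery, but it means only that the group held as many classes as it had timetabled.

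There is also a plain fault of form. An indicator of effective classes should rise as more of the planned classes are held. As written, it falls towards 1 as delivery improves, exceeds 1 when classes are missed, and is undefined for a group that holds none, which is the case monitoring most needs to detect.

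What is at stake is the reading of implementation. The general objective covers the functionality of the intervention as well as its effect, and the process indicators are the means of judging the former. Class duration does not fill the gap, because minutes per class give weekly exposure only when multiplied by the number of classes held per week.

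**Working it through.** The protocol states no value for this indicator, so there is no figure to reproduce. The check is ratio arithmetic.

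**Inputs**
- Standard: at least 2 classes per group per week (Table 5).
- Indicator: programmed/realized, per group (Monitoring and evaluation).
- Weekly counts programmed (P) and realized (R): not given in the protocol. Those below are assumptions, with P from 1 to 3 and R from 0 to 2.

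**Formulas**
- As written: P/R
- Turned the right way up: R/P
- Against the standard: R/2

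| P | R | P/R | R/P | R/2 | Standard met? |
|---|---|---|---|---|---|
| 1 | 1 | 1.00 | 1.00 | 0.50 | no |
| 2 | 2 | 1.00 | 1.00 | 1.00 | yes |
| 3 | 2 | 1.50 | 0.67 | 1.00 | yes |
| 2 | 1.6 | 1.25 | 0.80 | 0.80 | no |
| 2 | 1 | 2.00 | 0.50 | 0.50 | no |
| 2 | 0 | undefined | 0.00 | 0.00 | no |

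**Reading the table**
1. Rows 1 and 2 have the same indicator value in either direction, although one group receives twice as many classes as the other and only that group meets the standard.
2. Rows 2 and 3 receive the same 2 classes and both meet the standard, yet row 3 shows a shortfall.
3. Suppose one group moves from row 1 to row 4. Classes held rise by (1.6 − 1)/1 = 60%. R/P falls from 1.00 to 0.80, and P/R moves away from 1.00 to 1.25. Both read as worse delivery. R/2 rises from 0.50 to 0.80.
4. Rows 2, 4, 5 and 6 all have P = 2, and there R/P equals R/2. The scaling problem therefore disappears if every group programmes exactly 2 classes. The inversion remains.

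**The case against.** The strongest reply is that the two places do not contradict each other. Table 5 itself promises monitoring against 2 per week. Programmed versus realized is an ordinary fidelity measure, and nothing says that it replaces the weekly count. The indicator list is expressly open. Table 5 is introduced as possible strategies from an earlier project, some of which may be modified. Both parts of the ratio have to be recorded anyway, so realized classes can be set against 2 later.

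Most of this stands, and it limits the point to the definition of one listed indicator. It does not remove the point. The list offers further indicators for actions still to be designed, whereas this one is already defined, and no listed indicator expresses the standard. Improving physical education classes is also among the strategies named outside Table 5. None of the reply answers the inversion.

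A reader might go further and infer that the indicator will rank the arms the wrong way round, or make a successful strategy look like a failure. The documents do not support that. They give no timetable figures and no sign that timetables differ by arm. Table 1 shows the same 8:00 to 12:30 day in all six schools, which does not settle the question either way. They do not say that the strategy changes the number of classes programmed; the sentence on principals is incomplete. No between-arm comparison of this ratio is planned, although indicators are to be drawn up for the comparison schools. The move from row 1 to row 4 is a conditional illustration only.

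**Conclusion.** The point holds as a fault of definition. The listed indicator is inverted, and in either direction it cannot show whether a group receives at least 2 classes per week. The inversion is certain from the text. The size of the scaling problem is unknown: it is nil if every group programmes exactly 2 classes, and under the assumed counts it is large enough to give the same score of 1.00 to half delivery and to full delivery. It matters in practice only if timetables differ between schools or change during the project.

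The impact results are not affected. The ratio is not among the main outcome variables in the Information analysis plan. The length and quality of classes listed in Table 6, and the SOFIT observations made in both arms, do not depend on it.

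**What to change.** In the indicator list under Monitoring and evaluation, replace the present ratio with three lines:

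1. **Primary line:** classes realized per group per school week, reported against the standard of 2. Either realized/2 or the share of group-weeks with at least 2 classes would serve. The share is the stricter form: weeks of 3 and 1 classes average (3 + 1)/2 = 2, so realized/2 gives 1.00, while only 1 of the 2 weeks meets the standard. Report it over the same weeks in all six schools, with effective minutes realized beside it.
2. **Secondary line:** realized/programmed, with the fraction turned the right way up, as the fidelity measure.
3. **Secondary line:** the number programmed, so that differences or changes in timetable are visible.

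The parent-attendance ratio in the same list is also written with the total over the number attending, and can be turned over in the same edit.

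The cost is a few lines of wording and a little extra tabulation. Programmed and realized counts and class duration are already needed for the listed indicators, and Table 5 already implies a weekly record. This assumes that the monitoring promised in the comparison schools covers the same counts, which the wording should state.
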